3.5 Analysis of Safety Endpoints

3.5.1 Adverse Events

An overview of AEs, which includes subject incidence of TEAEs, treatment-related TEAEs, serious TEAEs, TEAEs by toxicity grade and TEAEs leading to permanent discontinuation of treatment. For TEAEs presented by toxicity grade, the worst grade during the clinical study will be presented for each subject.

The subject incidence of TEAEs, treatment-related TEAEs and TEAEs leading to permanent discontinuation of treatment will be summarized by system organ class and preferred term. Treatment-emergent AEs will also be summarized in a table by toxicity grade. For TEAEs presented by toxicity grade, the worst grade for each event during the clinical study will be presented for each subject.

All AEs will be presented as a listing by subject. TEAEs leading to treatment discontinuation will be provided in a separate listing.

3.5.2 Clinical Laboratory Evaluations

Clinical laboratory results will be summarized by type of laboratory assessment (hematology, chemistry, endocrine), timepoint, and treatment. Summary statistics for actual values and changes from baseline will be tabulated by analysis window. Shifts from baseline clinical laboratory values based upon the normal range will be tabulated for each post baseline sample timepoint. These tables will utilize the normal ranges provided for the individual sample.

3.5.3 Vital Signs

The observed data at baseline and change from baseline for each measurement day will be summarized with descriptive statistics.

3.5.4 Electrocardiogram Results

The overall ECG assessment (abnormal or normal) will be summarized by treatment and analysis window. The QTcF values will be summarized by treatment and analysis window as both the QTcF value and change from baseline. A summary of the number of subjects with a value > 450, 480 and 500, and the numbers of subjects with change from baseline values > 30 and 60 by treatment and analysis window will be produced.

3.6 Pregnancy

A listing of positive pregnancy tests results will be produced.

3.7 Pharmacokinetic Analyses

Plasma concentrations at week 10 will be summarized. The bioanalytical laboratory will provide the plasma concentration data for serlopitant and 3 metabolites in ng/mL. Plasma concentrations will be converted to nmol/L (nM) by the Statistician using the following equation:

$$\text{Plasma serlopitant concentration in nM} = [(\text{plasma serlopitant concentration in ng/mL}) / (\text{MW of } 555.54 \text{ ng/nmol})] \times (1000 \text{ mL/L})$$

The same conversion will be followed for each metabolite concentration using the MW of **CCI** ng/nmol. Results will be summarized using Geometric Mean and Coefficient of variation (CV). The formulas used are shown below. Below BLQ values will be set to ½ of the BLQ values (i.e., **CCI** ng/mL = **CCI** nM).

Geometric Coefficient of Variation Formula:

$$\text{Geo CV} = \sqrt{\exp(\ln(\text{GeoSD}))^2 - 1} \times 100\%$$

Geometric Mean Formula:

$$\text{Geo Mean} = \sqrt[n]{y_1 \times y_2 \times y_3 \times \dots \times y_N} = \exp\left[\frac{\ln(y_1) + \ln(y_2) + \dots + \ln(y_N)}{n}\right]$$

Geometric Standard Deviation Formula:

$$\text{Geo SD} = \exp(\text{SD}(\ln(y_1) \ln(y_2) \ln(y_3) \dots \ln(y_x)))$$

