2.3 Study Endpoints

The study endpoints are listed below, with greater detail concerning these endpoints provided in [Sections 2.3.2 to 2.3.8](#).

Primary Efficacy Endpoint

The primary efficacy endpoint is the WI-NRS 4-point responder rate at Week 10.

Secondary Efficacy Endpoints

The key secondary efficacy endpoints are as follows:

- WI-NRS 4-point responder rate at Weeks 2, 4, 6, and 8
- WI-NRS 3-point responder rate at Weeks 2, 4, 6, 8, and 10
- Change from baseline in WI-NRS at Weeks 2, 4, 6, 8, and 10
- Change from baseline in daily WI-NRS scores through Week 2
- Change from baseline in WI-VAS at Weeks 2, 4, 6, and 10

Safety Endpoints

Safety endpoints include the following:

- Incidence of TEAEs and SAEs
- Changes from baseline in clinical laboratory parameters following study drug exposure
- Changes from baseline in vital sign and ECG parameters following study drug exposure
- Plasma concentrations of serlopitant and metabolites

Exploratory Endpoints

The exploratory endpoints include the following:

- Change from baseline in the Epworth Sleepiness Scale (ESS) to Weeks 2, 4, 6, and 10
- Change from baseline in Static Patient Global Assessment of Itch Severity (sPGA) to Weeks 2, 4, 6, and 10
- Patient Global Impression of Change in Itch Severity (PGIC) at Weeks 2, 4, 6, and 10

2.3.1 *Endpoint Data Capture*

The study endpoints will be captured within the eDC system, from central laboratories, within the IRT system, or a subject eDiary (see [Table 2](#)). The eDiary will be used to capture the WI-NRS data daily. From these measures the primary endpoint will be created. This system will also calculate and provide two measures to the study sites that are required for eligibility determinations: eDiary compliance and baseline 1-week average WI-NRS score.

Table 2 Data Capture Systems

Examination	eDC	Central Laboratory	IRT system	eDiary
Demographics	X			
Paper WI-NRS	X			
Daily WI-NRS				X
WI-VAS / ESS / sPGA	X			
PGIC	X			
ECG	X	X		
Vital signs	X			
Medical history / prior medications	X			
Physical exam	X			
Concomitant medications	X			
Laboratory Results		X		
Urine pregnancy test	X			
PK blood draw		X		
Dispense / collect study drug	X			
AEs/SAEs	X			
Randomization			X	

2.3.2 *Worst Itch - Numeric Rating Scale*

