2.3.7.2 Other Safety Endpoints

- Vital signs:
 - Systolic Blood Pressure, Diastolic Blood Pressure, Heart Rate, Respiration Rate, Height, Weight, Temperature and presence of a clinically significant abnormal values.
- 12-Lead Electrocardiogram:
 - RR, PR, QRS, QT, HR, QTcB, QTcF, and the ECG interpretation. A central read cardiologist assessment of normal vs abnormal will be available as well as an investigator assessment of clinically significant vs not clinically significant.
- Physical examination abnormalities identified as preexisting before treatment will be recorded as medical history. Abnormalities identified after treatment will be recorded as adverse events.

- Laboratory samples will include:
 - Hematology, Chemistry, Immunochemistry and Urine Pregnancy.

2.3.8 *Pharmacokinetic Measurements*

There will be one PK sample at the Week 10 visit. The plasma concentrations of serlopitant and metabolites M1/M1a, M2/M2a and M3 will be determined.

2.4 **Study Day and Visit Windows**

Summary tables will report data based upon the protocol scheduled time points (Baseline, Weeks 2, 4, 6, 10 and Follow-up). Assessment will be assigned to these time points based upon the study day they are performed on. The derivation of study day depends upon whether the event occurred prior to or after treatment. This results in the first day of treatment being on day 1 and the day prior to the first day of treatment being day -1. For events that occur prior to the first day of treatment the following definition is used,

$$\text{Study day} = \text{date of assessment} - \text{date of first treatment}.$$

For events that occur on or after the first day of treatment, a plus one is added,

$$\text{Study day} = \text{date of assessment} - \text{date of first treatment} + 1.$$

The analysis windows used to report non-daily endpoints are outlined in [Table 3](#). If more than one assessment is available within the range, the assessment closest to the target day is reported for the analyses window. If two observations exist with the same distance to the target day, the first observation is used.

Table 3 Analysis Windows

Visit	Range	Target Day
Screening	< Day - 7	First
Baseline	Day -7 to Day 1	Day 1
Week 2	Day 2 to Day 21	Day 15
Week 4	Day 22 to Day 35	Day 29
Week 6	Day 36 to Day 57	Day 43
Week 10	> Day 57	Day 71

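### As printed in SAP 3.7, the geometric CV formula reduces to sqrt(GeoSD² − 1), which is not the log-normal geometric CV and is too large whenever the log-scale SD is below 2

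*SAP*

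**What the plan says.** SAP Section 2.3 lists "Plasma concentrations of serlopitant and metabolites" among the safety endpoints. The data are sparse. According to SAP Section 2.3.8, "There will be one PK sample at the Week 10 visit", and serlopitant and its metabolites are measured in it.

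SAP Section 3.7 sets out the summary: "Results will be summarized using Geometric Mean and Coefficient of variation (CV"). It then says "The formulas used are shown below", so the formulas are instructions to the programmer and not background. Two of them matter here:

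- Under "Geometric Coefficient of Variation Formula", the expression beneath the square root sign reads, in the extracted notation, "\exp(\ln(\text{GeoSD}))^2 - 1} \times 100". Both round brackets close before the exponent.
- Under "Geometric Standard Deviation Formula", GeoSD is the exponential of the standard deviation of the logged concentrations.

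The same section says of low concentrations: "Below BLQ values will be set to ½ of the BLQ values". The numerical limit is redacted.

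**The concern.** ln(GeoSD) is the standard deviation on the log scale. The usual geometric CV squares that quantity first and exponentiates the square. As printed, the exponential is taken first and the result is squared. The exp and ln then undo each other, and what remains is a function of GeoSD that is not a coefficient of variation.

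At stake is a reported number. A programmer who follows the brackets gets one CV, and a second programmer who knows the standard form gets another. In that disagreement the SAP text would support the wrong one. The affected output is the Week 10 concentration table for serlopitant and three metabolites, where a moderately variable exposure could be reported as a highly variable one.

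**Working it through.** **Inputs.** The two formulas in SAP 3.7 are the only inputs from the documents. Neither the protocol nor the SAP states a CV, a GeoSD or a log-scale SD for serlopitant or its metabolites, so the plan has no figure to reproduce. The values of s below are assumptions, chosen to show the range.

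**Step 1: reduce the printed form.** Let s = SD(ln y). By the SAP's own definition GeoSD = exp(s), so ln(GeoSD) = s. Then

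- as printed: sqrt( [exp(ln GeoSD)]² − 1 ) = sqrt(GeoSD² − 1) = sqrt(exp(2s) − 1)
- log-normal CV: sqrt( exp([ln GeoSD]²) − 1 ) = sqrt(exp(s²) − 1)

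As a check on the second line, two million simulated log-normal values with s = 0.5 had an arithmetic CV of 53.3%, and the formula also gives 53.3%.

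**Step 2: where the two agree.** They are equal when 2s = s², that is at s = 0 or s = 2. For s between 0 and 2, 2s exceeds s² and the printed form is too large. Above 2 it is too small.

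**Step 3: one value in full.** At s = 0.5:

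- standard: sqrt(exp(0.25) − 1) = sqrt(0.2840) = 0.533, or 53.3%
- as printed: sqrt(exp(1.0) − 1) = sqrt(1.7183) = 1.311, or 131.1%
- ratio: 131.1 / 53.3 = 2.46

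**Step 4: across assumed values of s.**

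| s (assumed) | Standard CV | CV as printed | Ratio |
|---|---|---|---|
| 0.1 | 10.0% | 47.1% | 4.69 |
| 0.2 | 20.2% | 70.1% | 3.47 |
| 0.3 | 30.7% | 90.7% | 2.95 |
| 0.5 | 53.3% | 131.1% | 2.46 |
| 0.8 | 94.7% | 198.8% | 2.10 |
| 1.0 | 131.1% | 252.8% | 1.93 |
| 1.5 | 291.3% | 436.9% | 1.50 |
| 2.0 | 732.1% | 732.1% | 1.00 |
| 2.5 | 2273.8% | 1214.1% | 0.53 |

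Solving for the ratio gives exactly 3 at s = 0.288 (true CV 29.4%) and exactly 2 at s = 0.914 (true CV 114.2%).

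**Step 5: effect of the rule for values below the limit.** Replacing low values by half the limit can widen the log-scale spread and so move the ratio. As an illustration only, take 90 samples with s = 0.5 before substitution and put 5 to 10 of them at 4 to 6 log units below the centre. The resulting s runs from about 1.05 to 1.96, and the ratio falls to between about 1.9 and 1.0. The limit is redacted, so the documents cannot say whether this would occur.

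**The case against.** The strongest objection is that this may be a bracket slip, or not the sponsor's slip at all. The point turns on where one exponent sits in an equation extracted from a PDF, and superscript placement is a detail that extraction can lose. The neighbouring formulas are also loose: the geometric mean mixes n and N, and the geometric SD runs the logs together without separators. Nobody has reason to write exp(ln(GeoSD)) for GeoSD, so the squared logarithm was almost certainly intended. This stands as a reason to look at the source document first. It does not make the formula acceptable as it reads, because the SAP presents it as the one to be used.

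A reader might also draw stronger conclusions, which the documents do not support:

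- **That reported variability will be inflated two- to three-fold.** That factor needs a value of s, and none is given. At s = 0.2 the ratio is already 3.47, at s = 1.0 it is 1.93, and above s = 2 it reverses. It also supposes that the formula is coded literally.
- **That the CV is the only measure of spread planned.** Section 3.7 names only the geometric mean and CV, but the defaults in SAP 3.1 and protocol Section 8 include standard deviation, minimum and maximum for continuous variables, and Section 3.7 does not expressly set them aside.
- **That the results could not be compared with other serlopitant studies.** Neither document shows a CV from another study or how one was calculated. A literal CV can also be inverted by anyone who knows it was used: GeoSD = sqrt(1 + CV²), so 131.1% returns GeoSD = 1.649, s = 0.5 and the standard 53.3%. Protocol 8.10 combines concentrations with other studies under a separate population PK plan, reported outside the study report, and nothing says that this CV feeds it.

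**Conclusion.** The formula as printed is not the geometric CV. The algebra follows from SAP 3.7 alone and needs no assumption about the data. If it is programmed literally, the reported CV is too high for any s between 0 and 2.

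The size is conditional on s, which the documents do not give. For true CVs of about 30% to 115%, taken as an assumption, the overstatement runs from about three-fold down to about two-fold. Smaller CVs are inflated more; the error vanishes at s = 2 and changes sign beyond it.

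Severity is low. The CV describes one Week 10 sample per subject and enters no efficacy test, decision rule or sample size calculation. The conclusion also rests on the exponent standing in the source document where it stands in the extracted text.

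**What to change.** 1. Check the position of the exponent in the source document. If it already lies inside exp( ), only the bracketing needs to be made unmistakable.
2. Print Geo CV = sqrt( exp( [ln(GeoSD)]² ) − 1 ) × 100%, or equivalently sqrt(exp(s²) − 1) × 100% with s = SD(ln y).
3. Confirm that the program for the PK table uses that form. One test value is enough: s = 0.5 should return 53.3%, and 131.1% shows that the literal form was coded.

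The cost is one corrected line in the SAP and one program check. No data collection, sample size or other analysis changes.
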